4.4.8 Limitations of the Study

Limitations of the study are that it is a single center study with a small patient population.

4.5 Risk Analysis

The risk analysis includes a description and analysis of all increased risks to the research subjects and how these risks will be minimized. The risks can be separated into three categories: procedural-related risks, device performance-related risks, and device material-related risks.

4.5.1 Potential Risks

4.5.1.1 Procedural-related risks

Procedural related risks including general and device specific procedural risks can result in several serious harms to the patient including contrast damage, allergic response, paraplegia, peripheral nerve damage, injury to access vessel, dislodging of thrombus, dissection of vessel,

embolism, branch artery or parenchyma damage of ischemia, inadvertent internal iliac occlusion or ischemic colitis, system effects including increased risk of morbidity and mortality, local effects at the access site including wound infection, hematomas, seromas, arterial or venous damage, failure to access the aorta, inaccurate deployment of devices, failure to deploy devices, and displacement of devices. These risks can be mitigated in a number of ways including strict adherence to the investigational protocol, patient eligibility criteria, procedures performed by trained and qualified physicians, use of standard surgical and endovascular techniques, and regular follow-ups. Although the risk is lowered by following these mitigation strategies, the risk cannot be completely eliminated. However, the potential benefit of the manifold system as compared to other surgical techniques outweighs the potential procedural related risks to the patient.

4.5.1.2 Material-related risks

Material related risks are risks that are associated with physical components of the stent graft including risks related to stent breakage, branch vessel stent crush, barb fracture, fabric wear, biocompatibility, and sterility. Risks of these components include vessel occlusion, embolism, component separation, migration, and infection. These risks can be mitigated several ways including careful case planning for patient selection, device placement, proper sizing, use of compatible components, and regular follow-ups to identify early evidence of migration or separation.

4.5.1.3 Performance related risks

There are performance risks of the modular components succumbing to material fatigue resulting in component separation, endoleak or endotension, graft occlusion, kinking, or migration. These risks can be mitigated several ways including adhering to industry standard

seal zone lengths, proper oversizing, lining branch stents with self-expanding stents, regular follow-ups to identify early evidence of migration or separation and allow for appropriate treatment, by the use of completion angiography coupled with cuffs, ballooning, or additional stent grafts if evidence of endoleak.

4.5.2 Mitigation of Risks

Significant care and thought has gone into designing The Valiant™ Thoracoabdominal Stent Graft System and investigational procedure for proper delivery and deployment of devices to minimize risks to patients to the greatest degree possible. The design of the stent graft is bifurcated to provide flow to uninterrupted blood flow to the visceral and infrarenal segments during the repair process, negating the need for aortic clamping utilized in open repair. Additionally, the design of the stent graft system is modular to allow for bailouts and staging of the procedure throughout device deployment. At any point in the procedure, the patient still has the opportunity for alternative treatments such as open surgical repair or other endovascular techniques.

All efforts will be made to minimize the identified risks including:

- Adherence to eligibility criteria and screening procedures to ensure that appropriate patients are selected and enrolled.
- Adherence to the investigation protocol and clinical methods for case planning, device modification, and implantation will be followed.
- Patients will be carefully monitored throughout the study period.
- The investigator will evaluate the adverse events during the course of the study.

4.6 Monitoring Procedures

Study monitoring and auditing will be performed by experienced and appropriately trained personnel appointed by the sponsor/investigator to ensure that the investigation is conducted in accordance with FDA IDE regulations. Monitoring functions will be conducted by dedicated Clinical Research Monitors at Biomedical Research Alliance of New York (BRANY) ([name]). Monitoring will be performed according to procedure.

Informed Consent

- Review 100% of all informed consents to ensure:
- That the subject signed and dated the informed consent form for him/herself.
- A valid (current IRB-approved version) copy of consent form was used.
- Review documentation of informed consent process.

Protocol

- Confirm that the study staff is conducting the study in compliance with the protocol approved by the IRB.

Source Document Verification

- Review first five subject charts for:

- Trial eligibility. If there are any subjects that did not meet trial eligibility, then five additional charts will be monitored. These additional charts will be chosen randomly.
- Primary and secondary safety and efficacy data- If there are discrepancies/errors discovered with reporting this data, then five additional charts will be monitored. These additional charts will be chosen randomly.
- Any correction made to the source documents is dated, initialed, and explained. The original entry should not be obscured.
- The protocol specific source documents are on file.
- Source documents are completed in ink.
- Note to files are made for missing or incomplete data and to explain any discrepancies or additional comments.

Electronic Case Report Forms in Redcap or equivalent eCRF system

- Ensure the data reported on the eCRF is consistent with the source documents.
- Discrepancies between the source documents and eCRF are explained in a note to file or captured in a comment in the eCRF.

Adverse Events & Serious Adverse Events

- Monitor will review all subject research chart and medical records to ensure the following:

- All AEs and SAEs have been reported including any abnormal physical exam findings determined to be clinically significant.
- They have been reported in a timely manner defined as within ten (10) business days between the time the site staff became aware of the event to the time it has been recorded and entered in eCRF.
- AEs have been reviewed; attribution has been assigned and signed by investigator in a timely manner.
- Ensure any AEs and SAEs have been submitted to the IRB and FDA that meets IRB/FDA reporting criteria.
- All subject deaths have been reported appropriately.

Protocol Deviations

- Ensure all protocol deviations that meet reporting requirements have been reported to the IRB as well as reported in eCRF.

Investigational Product

- Ensure investigational product has been properly handled and stored.

Monitoring Intervals:

Monitoring will occur at regular intervals throughout the duration of the trial. Monitoring can be performed on-site or remotely

4.7 Reporting

All reports to FDA will be identified as SI-IDE Reports:

Deviations from the investigational plan: The sponsor-investigator will notify the reviewing IRB and FDA of any deviation from the investigational plan to protect the life or physical well-being of a subject in an emergency. The notice will be provided as soon as possible but no later than 5 working days after the emergency occurred. If the change or deviation may affect the scientific soundness of the investigational plan or the rights, safety or welfare of the subject, the sponsor will obtain prior IRB approval and also FDA approval for the deviation by submitting an IDE supplement.

Unanticipated adverse device effects: The sponsor-investigator will report the results of an evaluation of an unanticipated adverse device effect to FDA and all reviewing IRBs within 10 working days after the sponsor-investigator first receives notice of the adverse effect.

Withdrawal of IRB approval: The sponsor-investigator will notify FDA of the withdrawal of IRB approval of an investigation (or any part of an investigation) within 5 working days of receipt of the withdrawal of approval.

Progress report or annual reports: The sponsor will provide progress reports to the reviewing IRB and to the FDA using the suggested format provided at:

<http://www.fda.gov/MedicalDevices/DeviceRegulationandGuidance/HowtoMarketYourDevice/InvestigationalDeviceExemptionIDE/ucm046717.htm#sugforforidefin>

To describe the follow-up compliance for the study, the sponsor will include a table in the annual progress report:

Table 8. Annual progress report

		# (%)			Adequate imaging to assess the parameter*** # (%)				Events occurring before next interval # (%)				
Visit	Eligible for follow-up*	Subjects with data for that visit	CT	X-ray	Subjects with follow-up pending**	Size Increase	Endoleak	Migration	Fracture	Death	Conversion	LTF	Not due for next visit
Operative				N/A		N/A							
30 day													
6 month													
1 year													
Additional years													

*Eligible for follow-up = previous eligible for follow-up – (previous death + conversion + LTF + not due).

** Subjects still within follow-up window, but data not yet available.

*** Not the number of subjects with these reported events; the number with adequate imaging, such as paired size data to evaluate aneurysm growth.

Additionally, the sponsor will send an Interim Report for every five patients regardless of study arm, and within the report divide those 5 into their respective primary or expanded selection cohorts.

These reports will include basic information on the number of patients enrolled and treated and information on observed adverse events for any subgroups (e.g., device types, extents of disease, lesion types). These interim progress reports are meant to be summaries and not complete progress reports. Details will be captured in any adverse event reports and annual reports to the IDE.

Table 9: Enrollment summary*

	column for each subgroup	Total
Enrolled		
Treated		
Awaiting treatment		
Withdrawn (state reason)		

* A subject is considered enrolled after the device enters the body.

Summary

For each subgroup of patients, a brief narrative description of the procedures completed to date (e.g., how many had devices implanted successfully), any need for additional interventions, and the outcomes of any additional interventions will be provided.

Table 10: Treatment summary

	Number of patients	Procedural success	Perioperative death
One branch			
Two branches			
Three branches			
Four branches			
Total			

Adverse Events

Comments on the most commonly observed challenges or adverse events will be provided.

The following table is an example of how adverse event numbers may be presented for each subgroup. The list will include events observed in the study, not necessarily all that are listed in this example	1 st 5	2 nd 5	Additional groups	All
Aortic dissection				
Branch vessel embolism (renal, celiac, SMA, etc.)				
Branch vessel occlusion (renal, celiac, SMA, etc.)				
Branch vessel dissection (renal, celiac, SMA, etc.)				
External iliac dissection				
Interval iliac occlusion				
Ischemic colitis/Colon necrosis				
Late related death				
Late unrelated death				
Leg ischemia				
Lower extremity embolism				
Lower extremity paralysis				
MI				
Perioperative death				
Renal failure/impairment				
Respiratory failure				
Stroke				
Wound necrosis				

Table 6: Adverse Events

Study subjects who had multiple complications will be designated using symbols (#, *, +) or numbers.

Lessons Learned

The lessons learned from the beginning of the study (e.g., with respect to patient selection, methods to minimize adverse events) will be summarized. Procedures proposed or implemented to mitigate any risks or challenges that were observed during the study will be discussed, as well as any changes in outcomes based on experience gained during the study.

Recalls and device dispositions: The sponsor-investigator will notify FDA and all reviewing IRB's of any request that a sponsor-investigator return, repair, or dispose of any unit of an investigational device. The notice will be made within 30 working days after the request is made and will state why the request was made.

Final report: The sponsor-investigator will notify FDA and all reviewing IRBs within 30 working days of the completion or termination of the investigation. The sponsor-investigator will also submit a final report to FDA and all reviewing IRBs and participating investigators within 6 months after the completion or termination of the investigation. The suggested format for final IDE reports will be utilized in preparing the final report as described at:

<http://www.fda.gov/MedicalDevices/DeviceRegulationandGuidance/HowtoMarketYourDevice/InvestigationalDeviceExemptionIDE/ucm046717.htm#sugforforidefin>

Clinical Trial Database report: The sponsor-investigator with an applicable study registered with the National Institutes of Health (NIH) National Library of Medicine's (NLM) ClinicalTrials.gov will report results of the study within 12 months of the trial reaching its completion data regardless of outcomes or if the study is terminated early.

Failure to obtain informed consent: The sponsor-investigator will submit a report of the use of a device without first obtaining informed consent. The report will be made to FDA within 5 working days after receipt of the notice of such use.

Other reports: The sponsor-investigator will provide accurate, complete, and current information about any aspect of the investigation upon request from the reviewing IRB or FDA.

4.8 Oversight

This study will have oversight by a Data Safety Monitoring Board (DSMB) consisting of independent scientific and bio-statistical expertise, who are not participating as investigators in the study. The DSMB will monitor and evaluate the safety of subjects and progress of the study. The board will meet after every 5th patient enrolled in the primary study arm receiving the investigational device and annually during the follow-up period to review subject data. The board will also meet at unscheduled times according to clinical necessity. The data safety reports reviewed at each meeting will contain enrollment data and all documented adverse events experienced by the participants and treatment outcomes. The focus of the analysis is to determine whether enrollment should continue or be closed and whether the trials should continue as originally designed or require modification/amendment.

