3.9 Report of Prior Investigations Synopsis

The single center experience with the Visceral Manifold Thoracoabdominal Stent Graft System from Sanford Health ([name]; PS-IDE (G140207) were recently reported.¹ 29 patients were successfully treated between March 2012 and January 2016. Twenty-seven patients were followed up to 1 month, 21 were followed up to 6 months, 16 were followed up to 1 year, and 8 have been followed past 1 year thus far. Using the Crawford classification, there were 8 with a type 1/type 2, 6 type 3, 8 with type 4, and 7 with type 5. 97.3% (108 of 111) of target vessels were successfully stented and 99% (107 of the 108) target vessels remained patent throughout follow-up. 15 patients in this experience met inclusion criteria (identical to ours) and were enrolled in the primary arm and 14 did not meet inclusion criteria and were treated as compassionate use. The majority of this latter group would have been considered part of the expanded arm of our protocol. Specifically, 4 were emergency ruptures, 5 were chronic type B dissections, and the remaining 5 had suprarenal fixated stents or an occluded renal (total n=14). In the group meeting IDE inclusion criteria, there was an average length of stay of 7.5 days with no in-hospital or 30-day death, no cases of paraplegia, and one case of renal failure which resolved. There was one death at 11 months from a CVA. In the group not meeting IDE inclusion criteria, there was an average length of stay of 9.5 days, with no in hospital or 30-day death, two cases of paraplegia, and six cases of temporary or permanent renal failure.

When contrasted with open repair's significant complication rates and branch fenestrated device's significant anatomic and logistic limitations, the potential risk of the proposed novel graft does not outweigh the potential benefit of widened anatomic availability and improved patency rates. Given the potential benefits, we feel that it is justified to expose the target patient population to the potential risk. The non-clinical testing performed by Medtronic and the clinical results reported by Sanford Health show adequate safety of the device to support a clinical study.

4. Investigation Plan

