4.4 Protocol

This study is a prospective, single-center, non-randomized, multi-arm study to evaluate the therapeutic benefit of the Valiant™ Thoracoabdominal Stent Graft System. A total of 15 patients will be enrolled in this study.

- 6 subjects total will be treated in the primary study arm
- 9 subjects total will be treated in the expanded selection arm

The duration of the Investigation is anticipated as follows:

- Time to Complete Enrollment: 24 months
- Subject Follow-up Time: 5 years from last subject enrollment
- Total Duration Time: 7 years

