4.4.4 Follow-up Schedule

Patients included in the study will undergo follow-up at one month, six months, twelve months and then annually for five years. In the event of patient death, an autopsy may be performed.

Table 5. Follow-up Table

	Pre- op	Intra- op	Pre- discharge	Month						
				1	6	12	24	36	48	60
CTA/CT Scan with and without	X		X ⁸	X ²						
X-Ray	X ¹			X ¹						
Angiography	X ³	X								
Blood Tests	X ⁴	X ^{5, 6}	X ⁴							
Clinical Exam (including ABI)	X ⁷		X	X ⁷						
Branch Patency ² (duplex ultrasound)				X	X	X	X	X	X	X

- 1 Device X-ray may be requested to provide more focused imaging if potential device integrity issues are identified, but are unable to be confirmed, using CT. Per standard of care: A/P, Lateral and Bilateral oblique views.
- 2 In patients experiencing renal failure during follow-up, duplex ultrasound may be used in conjunction with non-contrast CT.
- 3 Pre-procedure angiography may be requested at discretion of film reviewer.
- 4 Blood tests include hemoglobin and creatinine; PTT and prothrombin collected pre-op and pre- discharge only.
- 5 Blood test for ACT.
- 6 Other intra-op labs for anesthesia.
- 7 Urine pregnancy test (for female patients of childbearing age)
- 8 If deemed necessary by the Principal Investigator

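### The only accrual-based DSMB meeting counts primary-arm subjects alone: with 6 planned it occurs once, and the 9 expanded-arm subjects never count toward it

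*Combined protocol and SAP*

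**What the plan says.** Section 4.8 (Oversight) gives the DSMB three routes to a meeting. Two are in one sentence: "The board will meet after every 5th patient enrolled in the primary study arm receiving the investigational device and annually during the follow-up period". The third is "The board will also meet at unscheduled times according to clinical necessity"; no criterion is attached to it.

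On content, 4.8 is broad: "The data safety reports reviewed at each meeting will contain enrollment data and all documented adverse events experienced by the participants and treatment outcomes". Nothing restricts those reports to the primary arm. One stated focus of the board's review is whether enrollment should go on or be closed.

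Section 4.4 plans 6 primary-arm subjects and states "9 subjects total will be treated in the expanded selection arm", 15 in all, over 24 months of enrollment. Section 4.7 (Reporting) has a second rule based on fives, for a different document: "the sponsor will send an Interim Report for every five patients regardless of study arm", split by cohort. That report belongs to a section that opens with reports to FDA, and it is not linked to a DSMB meeting.

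**The concern.** The board is meant to advise on whether enrollment continues, so it needs looks while enrollment is open. The one look that is certain to be tied to accrual depends on the smaller, lower-risk arm. Under section 4.4.2 the expanded arm admits ruptured and contained-rupture aneurysms, urgent or emergent presentation, subacute or chronic type B dissection, failure of two major organ systems, and creatinine above 2.0 mg/dL. These subjects could all be treated without bringing a count-triggered meeting any closer.

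The other two routes do not reliably fill the gap. Unscheduled meetings depend on someone judging that one is needed. Annual meetings follow the calendar, and the start of the follow-up period is not defined. If annual meetings began only after enrollment closed, the single primary-arm trigger would be the only fixed look at which enrollment could still be changed.

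**Working it through.** **Inputs.** Primary arm 6, expanded arm 9, total 15 (4.4). DSMB count: every 5th primary-arm subject receiving the device (4.8). Interim-report count: every five patients in either arm (4.7). The total reproduces: 6 + 9 = 15, with the expanded arm 9/15 = 60%.

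**Number of count-triggered meetings.**
- As written: floor(6/5) = 1, at primary subject 5 with one primary subject left. A second would need a 10th primary subject.
- Counting both arms: floor(15/5) = 3.
- Latest case as written: 4 primary + 9 expanded = 13 subjects treated before the subject who triggers the meeting.

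**Expanded subjects already treated at the trigger.** The documents give no accrual order, so both calculations below rest on assumptions. Let K be the number of expanded subjects treated before the 5th primary subject. K can be anything from 0 to 9.

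*Assumption A: all orders of the 15 subjects equally likely.*
- P(K = k) = C(k+4, 4) × (10 − k) / C(15, 6), with C(15, 6) = 5005.
- E[K] = 9 × 5/7 = 6.43.
- P(K ≥ 5) = 1 − (10 + 45 + 120 + 245 + 420)/5005 = 4165/5005 = 0.832.
- P(K = 9) = 715/5005 = 0.143.
- Mean total treated at the trigger = 5 + 6.43 = 11.43, leaving 15 − 11.43 = 3.57 untreated.

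*Assumption B: each new subject is expanded-arm with constant probability p until that arm is full.* Then K = min(9, N), where N is negative binomial: the number of expanded subjects before the 5th primary subject.

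| p | E[K] | P(K = 9) |
|---|---|---|
| 0.40 | 3.30 | 0.03 |
| 0.50 | 4.75 | 0.13 |
| 0.60 | 6.37 | 0.35 |
| 0.75 | 8.35 | 0.79 |

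**Both arms counted, under assumption A.** Expected expanded subjects treated are 5 × 9/15 = 3.0 at the first look and 10 × 9/15 = 6.0 at the second. At the first look there can never be more than 5, whatever the order.

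**When the annual meetings start.** Section 4.4 lists "Subject Follow-up Time: 5 years from last subject enrollment", after 24 months of enrollment. Section 4.4.4 says "Patients included in the study will undergo follow-up at one month, six months, twelve months and then annually for five years", which starts the clock for each subject. On the first reading no annual meeting falls within enrollment; on the second at least one could. Section 4.8 does not say which applies.

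**Prior experience (3.9).** Among 14 prior subjects who did not meet criteria there were "six cases of temporary or permanent renal failure", against 1 of 15 (resolved) among those who did: 43% against 7%, two-sided Fisher p = 0.035. Paraplegia was 2/14 against 0/15, p = 0.22. Neither group had an in-hospital or 30-day death, and only a majority of the 14 would fit this trial's expanded arm.

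**The case against.** The strongest reply is that the worst case depends on a strained reading. The line in 4.4 about five years from the last enrollment belongs to a duration projection (24 months + 5 years = 7 years). It tells the reader when follow-up ends, not when it begins. Sections 4.4.4 and 4.4.5.6 start follow-up at one month for each subject, so the more natural reading puts at least one annual meeting inside enrollment, with every participant's adverse events before the board. This has force: the post-enrollment reading is a possibility and should not be treated as the plan. It does not remove the gap, because an annual meeting is not tied to how many expanded subjects have been treated.

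The plan also has other safeguards. The synopsis requires IRB concurrence for expanded-arm treatment (4.4.2 repeats this only for the route based on another documented reason). Unanticipated device effects are reported to FDA and the IRBs within 10 working days, and the monitor checks all subjects' records for adverse events. These are real protections, but none is an independent board reviewing accumulating data.

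The accrual figures rest on assumed arrival orders, and the results vary widely with them. That is correct; they show only how late the look could be. The renal-failure comparison is one outcome chosen after the fact, it includes temporary cases, and paraplegia in the same data is not significant. It should carry no weight beyond illustration, since the eligibility criteria alone show that the expanded arm is at higher risk.

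Finally, counting both arms leaves the unscheduled-meeting criterion undefined, does not ensure that the fifth subject's 30-day outcome is known when the board meets, and adds a third look too late to affect enrollment. All of this is true. The first two looks are where the gain lies.

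**Conclusion.** The concern holds. As written, accrual triggers one DSMB meeting, and 9 of 15 subjects, in the arm that is higher-risk by its own criteria, cannot bring it forward. This follows from 4.4 and 4.8 alone and needs no assumption. How late the meeting falls does depend on accrual order: the mean is 6.4 of 9 expanded subjects under random order and 3.3 to 8.3 under the constant-probability assumption, with 0 to 9 possible.

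The finding is limited to timing. The board does not meet only once, and it is not blind to the expanded arm. Sections 4.7 and 4.8 use different bases for a count of five, the independent board has the narrower one, and the documents give no reason. This is a design weakness that should be corrected on patient-safety grounds; it is not evidence of harm.

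**What to change.** In 4.8, replace the primary-arm count with a count of every fifth patient who receives the device in either arm, and have results presented by arm. Keep the annual and unscheduled meetings. Add one statement on whether the annual meetings run from the first subject's follow-up or only from the last enrollment.

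This aligns 4.8 with the count already used in 4.7 and puts meetings after subjects 5, 10 and 15, the first two while enrollment is still open.

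The cost is one amended sentence, one clarification and about two extra meetings of an existing board (3 − 1 = 2). Each meeting needs the full adverse-event listing that 4.8 calls for, because the 4.7 interim reports are only summaries. Sample size, eligibility and endpoints are unchanged.
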